6.1.4 Pharmacodynamic Variables

The pharmacodynamic parameters will be recorded at the time points mentioned in the table of assessments in the CSP section 7.

In both Parts A and B, mean and absolute value change from baseline at each post-baseline measurements for

Bond and Lader Visual Analogue Scale (VAS)

The Bond-Lader VAS will be used to rate subjects' feelings in terms of 16 dimensions. The dimensions will be presented as 100 mm lines, the 2 extremes of the emotion (i.e., 'alert' and 'drowsy') written at each end, and subjects will be asked to record their current state on each line.

The Bond-Lader VAS will be analyzed using 3 factor scores: alertness, contentedness, and calmness. Calculation of these 3 scores is based on the main factors resulting from statistical factor analysis. A high score indicates impairment.

1. Alertness (9 subscales): $[Q1 + Q3 + (100 - Q4) + Q5 + (100 - Q6) + (100 - Q9) + Q11 + (100 - Q12) + Q15] / 9$
2. Contentedness (5 subscales): $[Q7 + (100 - Q8) + Q13 + (100 - Q14) + (100 - Q16)] / 5$
3. Calmness (2 subscales): $[Q2 + (100 - Q10)] / 2$

Profile of Mood States (POMS):

POMS will be used to describe subjects' feelings with a questionnaire containing 65 words/statements. Feelings will be scored using different statement: "Not at All", "A Little", "Moderately", "Quite a lot", and "Extremely".

Korean Wechsler Adult Intelligence Scale-IV (K-WAIS-IV):

The K-WAIS-IV consists of an assessment of the cognitive ability using a core battery of 10 unique subtests (Block Design, Similarities, Digit Span, Matrix Reasoning, Vocabulary, Arithmetic, Symbol Search, Visual Puzzles, Information, and Coding) that focus on four specific domains of intelligence: verbal comprehension, perceptual reasoning, working memory, and processing speed.

PAREXEL International
Statistical Analysis Plan

Columbia Suicide Severity Rating Scale (C-SSRS):

The C-SSRS is a scale that captures the occurrence, severity and frequency of suicide-related thoughts and behaviors during the assessment period. The scale includes suggested questions to solicit the type of information needed to determine if a suicide-related thought or behavior occurred. The C-SSRS must be administered by appropriately trained site personnel. The C-SSRS will be administered at the times specified in Schedule of Procedures

In Part B only, PD parameters in plasma and CSF including:

- alpha synuclein oligomer
- total Tau
- phospho-Tau and
- ratio of CSF concentration/Plasma Cmax

6.1.5 Efficacy Variables

Efficacy will not be tested in this study.

6.2 Analysis Populations

6.2.1 Safety Population

The safety analysis set (SAF) will be the primary analysis set for all safety displays and consists of all subjects who received at least one dose.

6.2.2 Pharmacokinetic Population

The pharmacokinetic analysis set (PKAS) will be the primary analysis set for all PK displays and analyses, consists of all subjects from the SAF for whom sufficient plasma concentration data are available to facilitate the calculation of at least one PK parameter, had no important protocol deviations affecting the PK variables, as confirmed during a pre-analysis review of the data prior to database lock.

Data may/will be excluded (depending on the protocol and compound under study) from PK analysis (concentrations listed only) if any of the following criteria are fulfilled:

- Concomitant medication, which could render the plasma concentration-time profile unreliable

PAREXEL International

Statistical Analysis Plan

- The pre-dose concentration is greater than 5% of the corresponding C_{max} in any given treatment period (single dose cohort only).
- Subject vomits within 2 x the reported median T_{max} for the analyte (oral studies only).
- Subject has moderate or severe diarrhea within 2 x the reported median t_{max} for the analyte (oral studies only).

Any data excluded will be discussed in the CSR. Subjects who receive placebo will not be part of the PK analysis set.

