#### 8.1.3 *Analysis Sets*

Safety Analysis Set (SAF): The safety analysis set (SAF) will be the primary analysis set for all safety displays and consists of all subjects who received at least one dose.

Pharmacokinetic Analysis Set (PKAS): The pharmacokinetic analysis set (PKAS) will be the primary analysis set for all PK displays and analyses, consists of all subjects from the SAF for whom sufficient plasma concentration data are available to facilitate the calculation of at least one PK parameter, had no important protocol deviations affecting the PK variables, as confirmed during a pre-analysis review of the data prior to database lock.

Pharmacodynamic Analysis Set (PDAS): The pharmacodynamic analysis set (PDAS) consists of all subjects from the SAF for whom sufficient data for neuropsychologic testing (Parts A and B) or plasma and CSF concentration data are available

(Part B) to facilitate the calculation of at least 1 PD parameter, had no important protocol deviations affecting the PD analysis, as confirmed during a pre-analysis review of the data prior to database lock.

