C_{max_D}	Maximum observed concentration divided by dose

*Parent drug only

This Table is applicable for Day7 of Multiple ascending dose (Part B).

All urine voided will be collected in the following intervals: pre-dose and 0-24 hours post-dose. Urine samples will be used for qualitative analysis of KM-819 and possible metabolic profiling, if appropriate, and will be reported separately. For cerebrospinal fluid (CSF) PK, the concentration of KM-819 will be listed and no other PK parameters will be calculated as there will be only one sample from each subject.

PAREXEL International
Statistical Analysis Plan

6.1.3.1 *Pharmacokinetic Parameter Calculation Methods*

PK parameters will be calculated by non-compartmental analysis methods from the concentration-time data using WinNonlin (WNL) Professional (Version 6.3 or higher) following these guidelines:

- Actual sampling times relative to dosing rather than nominal times will be used in the calculation of all derived PK parameters.
- There will be no imputation of missing data.
- Any subjects with more than one observed concentration data will be included in the PK analysis set provided that at least C_{max} and $AUC_{(0-t)}$ can be reliably calculated .
- If one or more non-quantifiable (NQ) values occur in a profile before the first measurable concentration, they will be assigned a value of zero concentration. If a single NQ value occurs between measurable concentrations in a profile, the NQ should generally be omitted (set to missing) in the derivation of pharmacokinetic parameters, statistical analysis, and the individual subject plots. If two or more NQ values occur in succession between measurable concentrations, the profile will be deemed to have terminated at the last measurable concentration prior to these NQs. For the purpose of individual subject plots, these NQs will be set to 0, and the subsequent measurable concentrations will be retained. For the derivation of pharmacokinetic parameters, these NQs and any subsequent measurable concentrations will be omitted (set to missing).
- PK parameters following single and repeat dose will be estimated according to the following guidelines:
 - C_{max} will be obtained directly from the concentration-time data.
 - t_{max} is the time at which C_{max} is observed.
 - λ_z will be estimated at terminal phase by linear regression after log-transformation of the concentrations:

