 - Only those data points that are judged to describe the terminal log-linear decline will be used in the regression.

PAREXEL International
Statistical Analysis Plan

- A minimum number of three data points in the terminal phase will be used in calculating λ_z with the line of regression starting at any post- C_{max} data point (C_{max} should not be part of the regression slope) and including C_{last} .
- The duration of time over which λ_z is estimated should generally be at least twice the subsequently estimated terminal phase half-life ($t_{1/2}$); exceptions to this duration made at the discretions of the PK scientist
- The adjusted correlation coefficient (R^2 adjusted) in general should be greater than 0.90. Any value less than 0.90 may be used at the PK Scientist's best knowledge and judgment.
- An appropriate number of decimal places should be used for λ_z to enable the reported value of $t_{1/2}$ to be calculated.
- $t_{1/2}$ will be calculated as $\ln 2 / \lambda_z$.
- AUC is calculated as follows:
 - The linear trapezoidal method will be employed for all incremental trapezoids arising from increasing concentrations and the logarithmic trapezoidal method will be used for those arising from decreasing concentrations.
 - $AUC_{(0-t)} = \int_0^t C(t) dt$. (AUCtau for repeat dose)
 - $AUC_{(0-\infty)} = \int_0^t C(t) dt + \int_t^{\infty} C(t) dt = AUC_{(0-t)} + C_t / \lambda_z$. (single dose only)
 - C_t is last observed quantifiable concentration.
- %AUC_{ex} will be calculated as $(1 - [AUC_{(0-t)} / AUC_{(0-\infty)}]) \times 100$.
- CL/F will be calculated as dose/AUC_(0-\infty), parent drug only.
- V_z/F will be calculated as CL/F/ λ_z , parent drug only.

The following PK parameters will also be derived using SAS

(version 9.2) or WinNonlin (WNL) Professional (Version 6.3 or higher) as deemed appropriate.

- R_{ac} Accumulation ratio calculated as:
 C_{max} (last dose interval)/ C_{max} (first dose interval).
 $AUC_{(0-t)}$ (last dose interval)/ $AUC_{(0-t)}$ (first dose interval).

PAREXEL International
Statistical Analysis Plan

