6.3.6 Protocol Deviations

Major protocol deviations will be defined at the data review meeting (DRM). Subjects with major protocol deviations might be excluded from the Pharmacokinetic population.

All protocol deviations will be recorded by the Investigator and will be listed by subject with each study part, by cohort. All protocol deviations will be discussed between PAREXEL and the Sponsor during the data review meeting before database lock in order to determine whether these may warrant exclusion of a subject from the statistical analyses.

Protocol deviations will be presented using the safety population.

All protocol deviations will be listed [Listing 16.2.2.1 (Part A) and Listing 16.2.2.2 (Part B)] by study part and cohort will include, the subject number, actual study day (if applicable), visit, time point, date/time, and a description of the deviation and classification (major or minor).

PAREXEL International Statistical Analysis Plan

Protocol deviations will be summarized [Table 14.1.3.1 (Part A) and Table 14.1.3.2 (Part B)] by treatment period for each study part for the subjects in the safety population.

Major protocol deviations will include the following:

- Deviation from the inclusion and exclusion criteria
- Deviation from study medication compliance in terms of medical conditions and/or AEs that may have interfered with drug absorption or with respect to factors likely to affect the primary endpoints
- Deviation from study procedure compliance; Non-compliance to study procedures or deviations from study procedures likely to affect the primary endpoints.

Time window deviations for PK blood sampling and safety or exploratory assessments will also be listed as protocol deviations. Tolerance windows for safety, PK blood sampling and exploratory assessments (when applicable) are provided in the final Windows Allowance Agreement (WAA).

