6.3.12.3 Assessment of Dose Proportionality

For Part A, dose proportionality [Table 14.2.3.1 (Part A)] will be assessed for parameters C_{max} , $AUC_{(0-t)}$ and $AUC_{(0-inf)}$ and for Part B [Table 14.2.3.2 (Part B)] for parameters AUC_{tau} and C_{max} on Day 1 and Day 7 using the pharmacokinetic population via the power model.

Individual concentration values will be used to perform a least-squares linear regression analysis, using the formula $\log_{pkvar} = \beta_0 \times \log_{dose} + \beta_1$, where ‘ \log_{pkvar} ’ represents the natural log transformed C_{max} , AUC_{last} or $AUC_{(0-inf)}$ and ‘ \log_{dose} ’ represents the natural log transformed dose. An estimate of the slope of the regression line and corresponding 95% confidence interval (CI) will be obtained.

The following SAS code will be used:

```
PROC REG DATA=pkparam alpha=0.05;  
  MODEL log_pkvar = log_dose / CLB;  
  RUN;
```

For each of the parameters C_{max} , AUC_{last} , $AUC_{(0-inf)}$ of part A and C_{max} , AUC_{tau} of part B a plot of the log-transformed concentration against the log-transformed dose will be constructed including the fitted line from the linear regression and the line of unity.

Dose proportionality plots of individual primary PK parameters will be displayed versus dose (log-log scale) along with the regression line and the 95% CI [Figure 14.3.1.1 (Part A) and Figure 14.3.1.2 (Part B)]. Plots of dose-normalized parameters versus dose [Figure 14.3.2.1 (Part A) and Figure 14.3.2.2 (Part B)] will also be provided.

Additionally, an analysis of variance (ANOVA) [Table 14.2.4] of the natural log-transformed dose-normalized PK parameters $AUC_{inf}/dose$ and $C_{max}/dose$ with log-transformed KM-819 dose as a covariate and subject as random effect, will be performed to estimate the slope of the effect of dose level on the PK parameter and its 95% CI.

Proc Mixed Data = data;

By parameter;

PAREXEL International
Statistical Analysis Plan

Class Subject;

Model log (pk Parameter) = log (dose)/ ddfm = kr outp=pred;

Random subject;

Estimate 'Mean Log Slope' lgdose 1 /cl alpha=0.05;

Run;

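### The SAP gives two entry rules for the PK analysis set: at least one PK parameter in 6.2.2, both Cmax and AUC(0-t) in 6.1.3.1, with no statement of which governs

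*SAP*

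**What the plan says.** Three places define who enters the PK analysis set.

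- **SAP 6.2.2** requires membership of the safety set, that "sufficient plasma concentration data are available to facilitate the calculation of at least one PK parameter", and no important protocol deviation affecting PK. It then lists grounds for excluding data: interfering medication, a high pre-dose concentration, vomiting and diarrhea. It also states the set's reach: "The pharmacokinetic analysis set (PKAS) will be the primary analysis set for all PK displays and analyses".
- **Protocol 8.1.3** has the same rule: enough data "to facilitate the calculation of at least one PK parameter, had no important protocol deviations affecting the PK variables".
- **SAP 6.1.3.1**, among the guidelines for calculating parameters, sets a condition: "Any subjects with more than one observed concentration data will be included in the PK analysis set provided that at least". The sentence then names two parameters, Cmax and AUC(0-t), and both must be reliable.

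All three refer to the PK analysis set. SAP 6.3.12.3 runs the dose-proportionality regressions "using the pharmacokinetic population via the power model".

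**The concern.** The first rule asks for any one parameter; the second asks for two named ones. Cmax, tmax and the individual concentrations do not depend on an AUC, yet the second rule removes all of them when AUC(0-t) is judged unreliable. With six active subjects in a cohort, one subject is a sixth of the data.

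The choice would also be made late. Cohort PK data are reviewed during escalation (Protocol 3.3 and 3.4), whereas the set is confirmed only at the review before database lock. A membership rule that can be read two ways leaves discretion at a point where one written rule would remove it.

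**Working it through.** The documents give no figure to reproduce. The check is a comparison of the two rules, followed by the effect of one lost subject.

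**Step 1. Apply both rules.** Take subjects who received KM-819 and have no important PK-related deviation.

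| Subject | SAP 6.2.2 and Protocol 8.1.3 | SAP 6.1.3.1 |
|---|---|---|
| Reliable Cmax, AUC(0-t) and AUCinf | in | in |
| Reliable Cmax and AUC(0-t), no reliable AUCinf | in | in |
| Valid Cmax, no reliable AUC(0-t) | **in** | **out** |
| No parameter calculable | out | out |

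Only the third row differs. The second row turns on what AUC(0-t) means. SAP 6.1.3.1 computes AUCinf as AUC(0-t) plus Ct divided by the terminal rate constant, where Ct "is last observed quantifiable concentration". For a single dose, AUC(0-t) therefore needs no terminal phase. For repeat dosing the SAP equates it with AUCtau.

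**Step 2. Look for text that settles the conflict.**

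- The exclusion list in 6.2.2 does not mention an unreliable AUC.
- Neither section refers to the other.
- SAP 6.3.12 gives a cross-reference for the PK population, but to 6.2.3, which is the PD population.
- The word 'reliably' has no criterion for AUC(0-t). The fit criteria in 6.1.3.1 concern the terminal slope.

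**Step 3. Identify the outputs that change.** If an unreliable AUC is not reported, the third-row subject adds nothing to the AUC summaries under either rule. What changes is:

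- the summaries of Cmax and tmax;
- the concentration summaries and plots;
- the Cmax regression;
- in Part B, the steady-state model of pre-dose concentrations.

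**Step 4. Size of losing one subject from a cohort.** Inputs: 6 active subjects per cohort (SAP 5), and the 95% confidence intervals planned for PK parameter means (SAP 6.3.12). On the log scale the half-width in SD units is t(0.975, n−1)/√n.

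- n = 6: 2.571/√6 = 1.05 SD
- n = 5: 2.776/√5 = 1.24 SD
- Ratio: 1.24/1.05 ≈ 1.18, or about 18% wider at equal SD

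Five subjects remain above the minimum of three that SAP 6.3.12 sets for parameter summaries, so the row is still reported.

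**Step 5. How likely is the third row?** Part A subjects are confined until Day 3, so only the 72-hour PK sample is taken after discharge. The 48-hour sample already lies 48/9.27 ≈ 5.2 predicted half-lives after the dose (Protocol 5.3 predicts 9.27 hours). Part B subjects stay until the last PK sample on Day 8. A usable Cmax without a usable AUC(0-t) should be rare. The documents give no expected number.

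**The case against.** **The governing rule can be inferred.** Section 6.2.2 is the population definition and matches the protocol, while the other sentence is one bullet among calculation guidelines. That is the sensible reading, and the fix adopts it. But no precedence is stated, and the bullet names the analysis set and uses the language of a condition. It could be read as merely sufficient for entry, but then it would add nothing to 6.2.2.

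**The room for an outcome-driven choice is limited.** Protocol 5.5 has analysis sets assigned before the overall randomization code is broken. This stands, although the bioanalyst is unblinded during escalation.

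**The affected analyses are modest.** This also stands. Dose proportionality is exploratory (Protocol 8.7.1), and in Part A the regression can draw on 5 × 6 = 30 young active subjects, so the 18% for one cohort does not carry over to the slope. The young-versus-elderly comparison is made in figures (SAP 6.3.12), with no test.

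**A stronger reading the documents do not support.** A reader might infer a second conflict from SAP 6.3.6, which describes some major deviations by their effect on the primary endpoints ("Non-compliance to study procedures or deviations from study procedures likely to affect the primary endpoints"), when the primary objective is safety. A deviation that matters only for PK might then seem to escape. The same section sends every deviation, not only major ones, to a review before lock that may exclude the subject. It counts conditions or AEs that may have disturbed drug absorption as major, and lists PK sampling-window deviations. The PK-specific criterion is already in 6.2.2.

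**Conclusion.** The inconsistency is real but minor. A subject with a valid Cmax and no reliable AUC(0-t) is kept under SAP 6.2.2 and Protocol 8.1.3 and dropped under SAP 6.1.3.1. One such subject in a cohort costs about 18% in half-width for the log-scale mean of Cmax. That figure assumes a full cohort of six and the same SD after the loss.

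Two further inferences go beyond the documents. A reader might suppose that the dropped subjects would be those with adverse events and high exposure, so that the loss biases Cmax. Nothing in the documents shows that AUC(0-t) would fail more often in such subjects. A reader might also try to state how far a cohort geometric mean would move. That needs a between-subject variability the documents do not give, and the direction depends on whether the lost value is high or low. Neither inference is part of this point.

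**What to change.** In SAP 6.1.3.1, replace the inclusion sentence with:

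> PKAS membership follows Section 6.2.2; each PKAS subject contributes every parameter that can be reliably calculated, and parameters that cannot are set to missing.

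This keeps the protocol's rule, so no protocol amendment is needed. The pointer to 6.2.3 in SAP 6.3.12 can be corrected to 6.2.2 in the same edit. SAP 6.3.6 needs no change for this purpose.

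The downside is that n may differ between Cmax and AUC within a table. The SAP's rule for fewer than three available parameter values already allows for varying counts. The change belongs before database lock; after that, the SAP's own route is an addendum.

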6.2.3 Pharmacodynamic Population

The PD analysis set (PDAS) consists of all subjects from the SAF for whom sufficient data for neuropsychologic testing (Parts A and B) or plasma and CSF concentration data are available (Part B) to facilitate the calculation of at least one PD parameter and had no important protocol deviations affecting the PD analysis, as confirmed during a pre-analysis review of the data prior to database lock.

6.3 Statistical Analysis Methods

6.3.1 Listings and Descriptive Statistics

All original and derived parameters as well as population characteristics will be listed and described using summary statistics. Frequency counts (number of subjects [n] and percentages) will be made for each qualitative variable. Descriptive statistics (n, mean, standard deviation [SD], median, minimum and maximum) will be calculated for each quantitative variable (unless otherwise stated). All listings will include repeated and unscheduled measurements.

Study Part A and Part B will be analyzed separately. For each part Tables, listings and figures will be generated separately.

The following rules will apply to any repeated measurements:

- If the repeated measurement occurs prior to study drug administration (in each treatment period if applicable) then the last obtained value (or last obtained set of triplicate measurements) prior to dosing will be used in the descriptive statistics and in the calculation of changes from baseline (for results measured in triplicate the mean of the triplicates will be used in the calculation of changes from baseline).

PAREXEL International

Statistical Analysis Plan

- If the repeated measurement occurs after study drug administration (in each treatment period if applicable) then the first (non-missing) value of any repeated measurements (or first set of triplicate measurements) will be used in the descriptive statistics and in the calculation of changes from baseline (for results measured in triplicate the mean of the triplicates will be used in the calculation of changes from baseline).
- If not otherwise specified, baseline refers to the last scheduled measurement (or mean of the set of triplicate measurements) before study drug administration (using the rules described above for repeated measurements).

All descriptive statistics will be presented by cohorts (dose). Subjects receiving placebo within each cohort will be presented as pooled treatment group.

All descriptive statistics will be presented by cohorts for measurements obtained during each treatment period. Descriptive statistics for all data obtained at Screening and follow-up will be presented.

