#### Exclusion Criteria for Elderly Subjects

##### Replacement for Exclusion No. 8 above

8. Subject has a mean pulse < 50 or > 90 bpm; mean SBP > 160 mmHg; mean DBP > 100 mmHg (measurements taken in triplicate after subject has been resting in supine position for 5 minutes; pulse will be measured automatically).

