1. STUDY OBJECTIVES

1.1 Primary Objective

- To evaluate the safety and tolerability of single and multiple ascending oral doses of KM-819 in healthy young adult male subjects.

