2. STUDY DESIGN

This is a first-in-human, single-center, randomized, placebo-controlled, double-blind, sequential group Phase 1 study in healthy subjects. The aim of this study is to evaluate the safety, tolerability, PK, and PD following the escalation of single and multiple doses of KM-819. The study will consist of 2 parts (Part A and Part B).

Part A Single Ascending Dose (SAD):

This part includes up to 5 cohorts of healthy young adult male subjects receiving single ascending doses (SAD)s of KM-819, and 1 additional single-dose cohort of elderly male or post-menopausal female subjects.

Up to 40 healthy young adult male subjects and 8 healthy elderly male or post-menopausal female subjects will be enrolled and randomized to receive either KM-819 or placebo.

Each of the 5 dose escalation cohorts consists of 8 healthy young adult male subjects; 6 subjects will receive single dose of 10 mg (1 x 10 mg tablet), 30 mg (2 x 10 mg tablet),, 100 mg (1 x 100 mg tablet),,

Kainos Medicine, Inc.

Final 1.0

KMCP-819-K101

14/Nov/2017

PAREXEL International
Statistical Analysis Plan

200 mg (2 x 100 mg tablet),, or 400 mg (4 x 100 mg tablet) KM-819 and 2 subjects will receive placebo.

Cohorts will be dosed sequentially with escalating doses, escalation to the next dose level will take place only after the safety, tolerability data, and available PK data from the previously treated dose cohort has been reviewed; see Section 3.4 of CSP for dose escalation criteria. In each of the 5 single dose cohorts, dosing of subjects will be sentinel, i.e., 2 subjects will be dosed on the first day (1 subject will receive active treatment and 1 subject will receive placebo) and the remaining 6 subjects will be dosed at least 24 hours after the first 2 subjects

After completion of the 5 dose escalation cohorts, 8 elderly male or post-menopausal female subjects will be enrolled into an additional cohort; 6 subjects will receive 200 mg KM-819 and 2 subjects will receive placebo.

Table 1 Dose Groups for Part A

[figure not shown]
KM-819 Dose (mg)	Subjects on KM-819 (n)	Subjects on Placebo (n)	Total Subjects in Group (n)	Age Group
10†	6	2	8	Young adult male subjects
30†	6	2	8	
100†	6	2	8	
200†	6	2	8	
400†	6	2	8	
200	6	2	8	Elderly male or post-menopausal female subjects

† Doses between the current planned range may be assigned or a dose may be repeated depending on safety, tolerability, and pharmacokinetic data from previous subjects and cohorts.

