5. RANDOMIZATION

In each dose cohort, 8 subjects will be randomized to have 6 subjects receiving KM-819 and 2 subjects receiving placebo in both Part A and Part B.

For further details of randomization scheme please refer the section 4.5.2 and 4.5.3 of the CSP.

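### SAP 6.3.1 pools placebo with no age split, which slightly contaminates the reference for the young dose groups and gives the elderly cohort a poor one

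*SAP*

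**What the plan says.** SAP 6.3.1 states: "Study Part A and Part B will be analyzed separately". Active subjects are summarised by cohort (dose). For placebo the rule is one sentence: "Subjects receiving placebo within each cohort will be presented as pooled treatment group". The PD section (SAP 6.3.13), the safety section (6.3.15) and the table titles (SAP Section 8) name no young and elderly placebo columns, and the protocol has no pooling rule that would add them. The SAP's young-versus-elderly displays are PK figures (6.3.12 and Section 9), and SAP 6.2.2 keeps placebo subjects out of the PK analysis set.

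Allocation is fixed within cohort (SAP Section 5): "8 subjects will be randomized to have 6 subjects receiving KM-819 and 2 subjects receiving placebo". Each part has young cohorts and one elderly cohort. For Part A, SAP Section 2 says "This part includes up to 5 cohorts of healthy young adult male subjects", and of the elderly cohort "6 subjects will receive 200 mg KM-819 and 2 subjects will receive placebo". Part B has up to four young cohorts and one elderly cohort, again with 2 placebo subjects each.

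The two populations have separate objectives. The primary one is "To evaluate the safety and tolerability of single and multiple ascending oral doses of KM-819 in healthy young adult male subjects" (SAP 1.1). Safety, tolerability, PK and PD in the elderly are secondary objectives (SAP 1.2).

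**The concern.** Because randomisation is within cohort, the randomised comparator for a young dose group is young placebo, and for the elderly active group it is elderly placebo. The documents themselves treat the two populations differently at entry:

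- **Blood pressure.** The elderly replacement for exclusion criterion 8 (Protocol 4.2) excludes at "mean SBP > 160 mmHg; mean DBP > 100 mmHg". The young limits are 140 and 90 mmHg.
- **Medical history.** Criterion 21 excludes young subjects with any clinically significant disease, but elderly subjects only when the disease is not well managed and stable.
- **Sex.** Elderly cohorts may include post-menopausal women, while young cohorts are all male. Criterion 9 sets the QTcF limit at 430 msec for men and 450 msec for women.

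Protocol 3.3 gives the purpose of placebo as supplying reference data for interpreting results. Safety and PD summaries are descriptive, so the reader's main between-group comparison is by eye, from an active column to the placebo column. If that column mixes ages, it matches neither population exactly. The mismatch is much larger for the elderly cohort.

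**Working it through.** **Inputs.** All counts come from SAP Sections 2, 4 and 5 and assume every planned cohort is filled: 8 subjects per cohort at 6:2, young cohorts 5 (Part A) and 4 (Part B), one elderly cohort per part. The documents give no age difference, SD, effect size or power, so D is left symbolic or shown over an assumed range.

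**1. The plan's own totals.** 5 × 8 + 4 × 8 = 72 young and 8 + 8 = 16 elderly, which agrees with SAP Section 4.

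**2. The placebo pool.** Part A: 5 × 2 = 10 young + 2 elderly = 12, so 2/12 = 16.7% elderly. Part B: 4 × 2 = 8 young + 2 elderly = 10, so 2/10 = 20% elderly.

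**3. Displacement of the reference.** If the elderly placebo mean differs from the young one by D, the pooled mean lies (elderly share) × D from the young mean and (young share) × D from the elderly mean.

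| Assumed D (SD units) | Young, A | Young, B | Elderly, A | Elderly, B |
|---|---|---|---|---|
| 0.5 | 0.08 | 0.10 | 0.42 | 0.40 |
| 1.0 | 0.17 | 0.20 | 0.83 | 0.80 |
| 1.5 | 0.25 | 0.30 | 1.25 | 1.20 |

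**4. Illustration in mmHg, absolute systolic pressure only.** Assume D = 15 (range 10-20). The young reference moves 15 × 2/12 = 2.5 mmHg (1.7-3.3) in Part A and 15 × 0.20 = 3.0 (2.0-4.0) in Part B. The elderly reference is off by 15 × 10/12 = 12.5 mmHg (8.3-16.7) in Part A and 15 × 0.80 = 12.0 (8-16) in Part B. With an assumed SD of 10, the standard error of a 6-versus-12 difference is 10 × √(1/6 + 1/12) = 5.0 mmHg, and of a 6-versus-10 difference 5.2 mmHg. The shift for the young groups is thus about half a standard error (2.5/5.0 and 3.0/5.2).

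**5. Adverse events.** One elderly placebo subject with an event adds 1/12 = 8 percentage points (Part A) or 1/10 = 10 points (Part B) to the placebo column beside the young doses.

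**6. What a split costs in precision.** SE of active (n = 6) minus placebo = SD × √(1/6 + 1/n), assuming a common SD.

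- Young, Part A: 0.500 SD with n = 12, 0.516 SD with n = 10.
- Young, Part B: 0.516 SD with n = 10, 0.540 SD with n = 8.
- Elderly, either part: 0.500 SD (A) or 0.516 SD (B) with the pool, 0.816 SD with n = 2.

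**7. Break-even for the elderly.** The pool has the smaller mean squared error while (young share × D)² is below the variance saved. In SD units the limit is D = √(0.816² − 0.500²)/0.833 = 0.77 in Part A and √(0.816² − 0.516²)/0.80 = 0.79 in Part B.

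**The case against.** Several points on the other side are sound.

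- **Change from baseline.** Vital signs, ECG and laboratory values are summarised as changes as well as absolute values (SAP 6.3.15), and the PD endpoints are changes. A constant level difference cancels in a change score, and a stable gap would already show in the baseline rows. This stands. What survives is any age difference in absolute values, in response over time or in adverse-event rates. Observed values are tabulated too, and adverse-event percentages have no baseline correction.
- **Nothing confirmatory rests on the column.** SAP 6.3.13.1 plans no formal PD analysis, and safety is descriptive. Escalation uses blinded review after each cohort and subject-level unblinding (Protocol 3.3 to 3.5). Listings by cohort identify the elderly placebo subjects. All of this stands, but listings do not repair a summary table.
- **The sentence may mean pooling inside each cohort.** That would keep ages apart. It is the weaker reading, since two subjects on the same treatment in one cohort need no pooling rule, but the text does not exclude it. It would leave each young dose group with 2 placebo subjects and an SE of √(1/6 + 1/2) = 0.816 SD. Either way the sentence needs rewording.
- **Two elderly placebo subjects make a weak column.** True. By step 7, the pool is the better elderly reference if D is below about 0.8 SD.

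A reader might also infer that the elderly are known to differ on renal chemistry or on the Coding subtest. The documents do not show this. Wider entry limits are not observed differences, and some elderly limits are stricter: pulse below 50 rather than 40 bpm is excluded, and so is a glomerular filtration rate below 60.

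**Conclusion.** The point holds as a modest defect of presentation. On the more natural reading of SAP 6.3.1, each part's placebo column is 17% (Part A) or 20% (Part B) elderly. It is a slightly contaminated reference for the young dose groups, carrying 17-20% of D. It is a poor one for the elderly cohort, carrying 80-83% of D. This applies to absolute values and adverse-event rates in safety and PD tables; PK displays and dose-proportionality models are untouched. It rests on all cohorts being filled and on that reading of an ambiguous sentence.

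Two stronger conclusions are tempting. One is that the primary objective in young men is compromised. The documents do not support that: the young pool is 80-83% young, and even the assumed 15 mmHg gap moves it by only about half a standard error. The other is that the elderly cohort will show a false blood-pressure gap of about 12 mmHg. That figure depends wholly on an assumed D, concerns absolute levels only, and vanishes from the change summaries if the level gap is constant. Nor is placebo the only control, because each subject's own baseline is another.

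**What to change.** Reword SAP 6.3.1 to state the pooling unit. Within each part, safety and PD tables should show:

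- placebo pooled across the young adult cohorts (up to 10 in Part A, 8 in Part B), as the reference for the young dose groups;
- elderly placebo (n = 2) in its own column beside the elderly active group;
- all placebo in a further column.

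The cost is extra table columns. The young comparison loses almost nothing in precision. The elderly comparison against its own placebo is imprecise (0.82 SD, against 0.50-0.52 SD with the pool), so the all-placebo column should be kept to let the reader see both.
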